PROTOCOL

Study Title:	Apremilast 30 mg BID combined with Dupilumab for the Treatment of Recalcitrant Moderate-to-Severe Atopic Dermatitis
Study Drug:	Oral Apremilast 30 mg BID
Sponsor :	[name] Tufts Medical Center Department of Dermatology [name] [contact] [contact] E-mail: [contact]
Coordinators :	[name] RN, [name]

Version and Date:

Version June 2, 2021

I. Aim and Hypotheses: The purpose of this study is to determine if apremilast as a combined treatment for atopic dermatitis will provide increased efficacy outcomes in subjects who are currently using the FDA approved therapy of dupilumab but have responded only partially or inadequately to this therapy. Our hypothesis is that adding apremilast will allow patients to go from an inadequate response to dupilumab to an adequate response defined as an Investigator Global Assessment (IGA) of 0 (clear) or 1 (almost clear).

II. Background and rationale:

Background and Rationale:

Dupilumab is FDA approved for atopic dermatitis and has activity against the shared alpha-chain subunit of the IL-4 and IL-13 receptor system. While type 2 inflammation is the predominant problem in atopic dermatitis, Th1 and TH17 inflammation is also part of the pathogenesis. Apremilast alone is unable to sufficiently block the dominant type 2 immune pathway in atopic dermatitis; however, apremilast can decrease multiple cytokine pathways through PDE4 inhibition. Apremilast blocks inflammatory mediators such as TNF- α , IL-12, IL-2 production in AD patients and may improve pruritus by this mechanism.^{1–3} We believe adding apremilast to patients already treated with dupilumab will lead to further improvement in atopic dermatitis and select out the patient population that will most benefit from apremilast. One study using apremilast 30 mg BID versus apremilast 20 mg BID as monotherapy for atopic dermatitis saw a clinical effect after 3 months in the 30 mg BID group only.⁴ We will be using apremilast in combination with dupilumab, and think the results may be synergistic.

Our hypothesis is that the addition of apremilast to dupilumab will allow patients with an inadequate response to dupilumab monotherapy to potentially achieve an Investigators' Global Assessment (IGA) score of 0 (clear) or 1 (almost clear).

2.2) Apremilast (CC-10004):

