 - v. Mean and percentage change from baseline in Eczema Area and Severity Index (EASI) score at week 16

Safety Endpoints:

Safety and tolerability will be evaluated according to the frequency and severity of adverse events and changes in physical examinations or vital signs.

II. Research Plan

A. Overall Study Design:

Open label phase 2 investigational study of efficacy and safety of apremilast 30 mg BID in chronic atopic dermatitis when added to the FDA approved treatment dupilumab for atopic dermatitis that is not providing adequate clinical responses. The study will have 1 phase:

• Open label treatment period apremilast 30 mg BID

Following informed consent, subjects will be screened on the basis of atopic dermatitis severity and inadequate treatment response to current therapies. IGA, BSA, pruritus NRS, EASI, complete physical examination, medical history, and concomitant medications will be reviewed. Eligible subjects will be administered treatment with apremilast 30 mg BID while continuing their prior inadequate atopic dermatitis treatment regimen. During the treatment phase, study drug will be provided in an oral form and will be titrated over 5 days and then taken twice daily thereafter. Subjects return to clinic for reevaluation. Efficacy endpoints will be assessed at weeks 2, 4, 8, 16, and 24. Week 16 is the last week of study drug dispensation. Efficacy and safety indices will be assessed as per the Schedule of Assessments.

Treatment Assignment and Randomization

No randomization will be used, as this is an open label study. There will be no blinding and investigators will have knowledge of the treatment each subject is administered.

All patients seen in the Tufts Dermatology Clinic during the enrollment period who are not currently responding to existing FDA approved atopic dermatitis therapy and thus have not achieved a IGA of 0 or 1 at screening, and meet all other inclusion/exclusion criteria, will be offered participation in the study.

B. Statistical methods:

Sample size: We will screen up to 20 patients to ensure that 16 patients complete the study.

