- 5. Subjects must fulfill criteria outlined in the following clinical categories:
 - Subjects must be currently using and experiencing an inadequate response to dupilumab which is FDA approved for the treatment of moderate to severe atopic dermatitis. An inadequate response is defined as an IGA of 2 or more.
 - At the time of screening, subject must have a partial or inadequate response to their current treatment regimen. A partial or inadequate response at screening is defined as having both of the following:
 - Not having achieved an Investigator's Global Assessment score of 0 (clear) or 1 (almost clear).
 - Subjects must be on dupilumab for at least 12 weeks and willing to continue on dupilumab on a stable dose (40 mg weekly or every other week) while also receiving the study drug
- 6. Females of childbearing potential (FCBP) must have a negative pregnancy test at Screening and Baseline. While on investigational product and for at least 28 days after taking the last dose of investigational product, FCBP who engage in activity in which conception is possible must use one of the approved contraceptive options described below:

Option 1: Any one of the following highly effective methods: hormonal contraception (oral, injection, implant, transdermal patch, vaginal ring); intrauterine device (IUD); tubal ligation; or partner's vasectomy;

OR

Option 2: Male or female condom (latex condom or nonlatex condom NOT made out of natural [animal] membrane [for example, polyurethane]; PLUS one additional barrier method: (a) diaphragm with spermicide; (b) cervical cap with spermicide; or (c) contraceptive sponge with spermicide.

- 7. Male subjects (including those who have had a vasectomy) who engage in activity in which conception is possible must use barrier contraception (male latex condom or non-latex condom NOT made out of natural [animal] membrane [for example, polyurethane]) while on study medication and for at least 28 days after the last dose of study medication
- 8. If receiving concomitant medications for any reason, must be on a stable regimen and willing to stay on a stable regimen. This includes emollients, which should stay stable throughout the study.

Exclusion criteria:

- 1. Prior hypersensitivity reaction or exposure to apremilast

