1. **Study Procedures**: At the initial visit, a Investigator's Global Assessment (IGA) of disease will be performed to determine if the patient meets the inclusion criteria. A score on the NRS Pruritus

scale will be determined. A thorough medical history and a review of prior/concomitant medications will be taken at the screening visit. A complete physical examination including weight and vital signs (temperature, blood pressure) will also be performed. At the following visits according to the Schedule of Assessments, a IGA, BSA, DLQI survey, vital signs, NRS pruritus scale, EASI, a complete or targeted physical exam and review of concomitant medications and adverse events will be performed. Additionally, drug dispensing and accountability will also occur at all visits after the screening visit according to the Schedule of Assessments.

- Lab monitoring is not standard of care for patients using apremilast in clinic settings for the treatment of psoriatic disorders. Patients with psoriasis are frequently prescribed apremilast in addition to psoriasis biologic injectables, and it is not standard of care to perform lab tests for these patients that is outside of what is recommended for monitoring the safety of their injectable biologic alone. Atopic dermatitis patients taking apremilast are not at any increased risk compared to psoriasis patients taking apremilast. Dupilumab is a biologic, but this specific biologic does not require lab monitoring. For these reasons, lab monitoring will not be performed during this study as it would cause research subjects to undergo unnecessary testing. However, for all patients taking apremilast, it is standard of care to monitor weight at treatment visits and to ask patients about adverse symptoms. Both of these will be performed during the study based on the schedule of assessments.
- 2. **Subject Timeline**: 24 week duration of study treatment.

F. Assessment of Subject Safety and Development of a Data and Safety Monitoring Plan

- AE data will be collected at each study visit by asking the subject about their symptoms. The PI will review all AE data as they are collected, and the PI will sign off on AEs during the study visit. The AEs for the subjects will be stored in the subject's study documents and updated at each study visit. AEs will be collected from the time of ICF signature through the end of the study at all study visits.

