- 13. Alternatives: An alternative is not to participate in the study. In the event the subject decides not to participate, the principal investigator and/or site staff can discuss other treatment options for plaque atopic dermatitis with the patient including the following:
 - a. Continuation of existing regimen without participation in this study

- b. Topical medications such as corticosteroids (triamcinolone, clobetasol, etc.), topical calcineurin inhibitors (tacrolimus, Protopic, etc), and Eucrisa (crisaborole)
- c. Oral medications for eczema include steroids (Prednisone, etc.), or immunosuppressants (CellCept, cyclosporine, etc.).
- d. Participation in a different clinical trial for another investigational product
- e. The study drug, apremilast, is not available at this time for atopic dermatitis. It is currently approved for the treatment of psoriasis and psoriatic arthritis. Dermatologists may attempt to gain insurance coverage for off-label prescribing of this medication for AD at the end of the study. Dupilumab is currently standard of care for AD, and can be prescribed at the end of the study by the subject's regular dermatologist
- 14. How new information will be conveyed to the study subject and how it will be documented: New information will be conveyed through IRB approved amendment to the Informed Consent form.
- 15. **Payment, including a prorated plan for payment**: Subjects will be paid \$50.00 per visit for this study. Subjects will be paid via clincard. Subjects will be paid after each visit attended. Subjects will not be paid for any missed visits. Subjects can make up to \$300.00 for completion of the entire study.
- 16. **Payment for a research-related injury**: Research related injuries at not anticipated in this study and if an injury does occur, an appropriate plan of action will be determined by principal investigator at that time.
- I. **Outcome**: Study results and outcomes will be prepared in a manuscript for peer-reviewed journal publication. Success will be determined as described above in the "objectives" section.
- J. Tissue banking considerations: Not applicable.

Schedule of Assessments

Protocol Activity	Visit 1: Screening/ Baseline ¹	$\frac{\text{Visit 2}}{\text{Week 2}} \\ \pm 3$	$\frac{\text{Visit 3}}{\text{Week 4} \pm}$	$\frac{\text{Visit }4}{\text{Week }8} \\ \pm 3$	$\frac{\text{Visit 5}}{\text{Week}}$ 16 ± 3	$\frac{\text{Visit 6}}{\text{Week}}$ 24 ± 3	Early Termi- nation

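### Could a subject already clear or almost clear before the first dose be counted as a responder?

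*Protocol*

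**What the plan says.** **Entry.** Inclusion criterion 5 (Protocol, II.C) has two main parts. The first names no visit: "Subjects must be currently using and experiencing an inadequate response to dupilumab", followed by "An inadequate response is defined as an IGA of 2 or more". The second is dated: "At the time of screening, subject must have a partial or inadequate response to their current treatment regimen". Two other places also date the check. Treatment Assignment and Randomization (II.A) describes candidates who "thus have not achieved a IGA of 0 or 1 at screening", and Study Procedures (II.E) says "At the initial visit, a Investigator's Global Assessment (IGA) of disease will be performed to determine if the patient meets the inclusion criteria".

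**Timing of baseline.** The Schedule of Assessments has a single column for Visit 1, headed as both screening and baseline. Its footnote 1 allows baseline on the same day or up to 4 weeks after screening. Criterion 6, by contrast, names both visits: "Females of childbearing potential (FCBP) must have a negative pregnancy test at Screening and Baseline".

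**Endpoint.** The Objectives and II.B define the primary endpoint as the proportion at IGA 0 or 1 at Week 16. Efficacy is analysed only in those who complete at least 16 weeks of treatment. The SAP repeats the response definition and the completer rule. Neither document makes response conditional on the baseline IGA. The hypothesis in section I is that "adding apremilast will allow patients to go from an inadequate response to dupilumab to an adequate response".

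**Baseline value.** Changes are taken from baseline (Objectives) or from pre-treatment (II.B). Assessments of Efficacy lists BSA at both screening and baseline.

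**The concern.** The hypothesis is about movement from IGA 2 or more to IGA 0/1, but the endpoint records only the state at Week 16. The two agree only if everyone is at 2 or more when dosing starts. If the threshold is checked only at screening and dosing begins up to 4 weeks later, a subject could improve by one grade on dupilumab alone (entry is allowed at IGA 2), start apremilast at 0/1, stay there, and be counted as a response to apremilast. In a single-arm study of 16 completers, one such subject could move the only primary estimate by several points, always upward.

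The pregnancy criterion adds to the impression of an omission, because it shows that the authors name the later visit when they want a check repeated. The same split visit would also give two pre-dose BSA values with no statement of which one is baseline.

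**Working it through.** **1. Is a separate baseline the planned route?** Payment (II.G, item 15) is 50 dollars per visit, and "Subjects will be paid after each visit attended", up to 300 dollars. 300 / 50 = 6 visits, which matches Visits 1 to 6 with screening and baseline combined. A separate baseline would be a seventh visit. This suggests that the combined visit is the norm, but it is an inference: footnote 1 allows both timings without ranking them, so the frequency of separate baselines is unknown.

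**2. Does the text admit a subject at 0/1?** Set side by side:

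- The dated statements (II.A, criterion 5 second part, II.E) fix the check at screening or the initial visit.
- Criterion 5 first part requires a current inadequate response, IGA 2 or more, with no visit named. If it applied only at screening it would largely repeat the second part.
- Overall Study Design (II.A) has eligible subjects start apremilast while staying on a regimen it describes as inadequate, which presumes inadequacy at dosing.
- IGA is taken at every study visit (II.B, Secondary Endpoints), so a separate baseline would produce a pre-dose IGA for the investigator to see.

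The timing is unstated, but nothing in the text admits a subject at 0/1.

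**3. What must happen for an effect?** All of the following: a separate baseline; movement to 0/1 within 4 weeks, after at least 12 weeks on dupilumab (criterion 5) and with no atopic dermatitis medication added after consent (Permitted Concomitant Therapy); dosing despite that IGA; completion of 16 weeks; and IGA 0/1 at Week 16.

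**4. Size for one affected subject.** Let r be the number of responders among the other 15 completers (assumed; the documents give no expected rate). The rate with the subject is (r+1)/16 and without is r/15, so the difference is (r+1)/16 − r/15 = (15 − r)/240.

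| r | With (exact 95% CI) | Without (exact 95% CI) | Difference, points |
|---|---|---|---|
| 0 | 1/16 = 6.3% (0.2 to 30.2) | 0/15 = 0% (0 to 21.8) | 15/240 = 6.25 |
| 4 | 5/16 = 31.3% (11.0 to 58.7) | 4/15 = 26.7% (7.8 to 55.1) | 11/240 = 4.6 |
| 8 | 9/16 = 56.3% (29.9 to 80.2) | 8/15 = 53.3% (26.6 to 78.7) | 7/240 = 2.9 |
| 12 | 13/16 = 81.3% | 12/15 = 80.0% | 3/240 = 1.25 |
| 15 | 16/16 = 100% | 15/15 = 100% | 0 |

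If another subject had taken the place, the difference is 1/16 = 6.25 points when that subject is a non-responder and 0 when a responder. The full range is therefore 0 to 6.25 points. The interval for 5/16 is 58.7 − 11.0 = 47.7 points wide, and for 9/16 it is 80.2 − 29.9 = 50.3 points wide.

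**5. How likely is at least one?** The documents give no rate. If every completer had a separate baseline (an upper bound) and each had an assumed chance p of being 0/1 both before dosing and at Week 16, the chance of at least one among 16 is 1 − (1 − p)^16: 27.6% at p = 2%, 56.0% at 5%, 81.5% at 10%, 92.6% at 15%. With same-day baselines it is zero.

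**The case for a change.** The best case for a change is that prevention is nearly free. Two sentences would apply the protocol's own threshold at the last pre-dose assessment and define baseline as the last pre-dose value. No new assessment is needed. Entry at IGA 2 is one grade from response, so a change within 4 weeks is not far-fetched. Study Procedures places drug dispensing at visits after screening, which leaves the visit structure less settled than the single column suggests. If separate baselines were common, step 5 shows that an affected subject need not be rare.

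Much of this stands as fact. The dated text does name screening, the endpoint would not catch such a subject, and the arithmetic is correct. What does not stand is the inference that the plan would go wrong without the two sentences. They would write down what criterion 5 already implies. The probabilities in step 5 rest on assumed rates applied as if every subject had a separate baseline, and on investigators dosing a patient whose recorded IGA contradicts an entry criterion.

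On the baseline value, where a Baseline visit exists the ordinary reading of change from baseline is the value from that visit. DLQI is already placed at Day 1, and only BSA is expressly listed at both visits. Nor would the sentences remove the larger weakness: a subject with fluctuating disease, dosed on the screening day, who drifts to 0/1 would still count as a responder.

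**Conclusion.** No change follows. This is a gap in wording that investigators and analysts would fill sensibly: hold IGA 2 or more up to entry, and use the Baseline-visit value as baseline. The effect is zero for same-day baselines, which the single schedule column and the six-visit payment cap suggest is the usual case. On the separate-visit route it is 0 to 6.25 points per affected subject among 16 completers, against exact intervals roughly 48 to 50 points wide at 5/16 and 9/16. The analysis is described as primarily descriptive, with no null rate or success threshold, so no stated decision depends on it. The individual subject listings promised in II.B could reveal an affected subject.

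This rests on reading the undated part of criterion 5 as holding up to entry, and on separate baselines being uncommon, which the documents suggest but do not state. If separate baselines proved frequent and subjects were dosed at 0/1, the size per subject would still be that given above.

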General statistical Methods: A clinical response to apremilast for the purposes of this study will be defined as an Investigator Global Assessment score of 0 (clear) or 1 (almost clear). The end points of the study will be assessed at Week 16. A period of 16 weeks was chosen, as this was the time frame utilized for primary endpoint reporting in the ESTEEM clinical program.^{6,8} An additional 8 weeks of study drug will be provided to assess enhanced clinical benefit with continued use at 24 weeks. A rate of incompletion and/or drop out of subjects has been factored in to assure great than 16 patients will complete the study.

The analysis will be primarily descriptive. Mean, standard deviation, median, minimum, maximum, and 95% confidence interval for mean will be provided for continuous variables. Changes and percent changes from pre-treatment to on-treatment time points will be calculated for continuous efficacy points. Graphical displays of changes over time may be presented for key outcomes. Counts, percentages, and 95% confidence intervals will be provided for categorical variables. Subgroup analyses, such as gender stratification and stratification based on baseline treatment regimens, will be performed to identify a patient population that achieves the most benefit.

Efficacy analyses will only use data from participants who complete at least 16 weeks of study treatment in order to evaluate the primary endpoint.

Efficacy:

Primary Endpoint

Patients' Investigator's Global Assessment $(IGA)^9$ will be assessed at weeks 2, 4, 8, 16, and 24, with the primary endpoint being the proportion of patients with an IGA of 0 (clear) or 1 (almost clear) at Week 16.

Secondary Endpoints

Secondary endpoints will be assessed according to the scale of the outcome variable of interest. BSA and Eczema Area and Severity Index¹⁰ will be assessed along with IGA at all study visits. For quality of life outcomes, the Dermatology Life Quality Index (DLQI)¹¹ will be used to assess changes from baseline in overall score will be provided. Assessment of outcomes of each protocol-scheduled time point (Weeks 2, 4, 8, 16, and 24) will be performed for each endpoint. Various schemes will be assessed for missing data imputation if needed. The change in the patient's Numerical Rating Scale for Pruritus (NRS) will be assessed.¹²

Background and demographic characteristics:

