Prior/Concomitant Medications

Subjects may take any medication that is not restricted by the protocol and would not be expected to interfere with the conduct of the study. As the purpose of this study is to evaluate the efficacy of apremilast 30 mg BID when combined with dupilumab, subjects must continue on a stable dose of dupilumab while also receiving the study drug.

All medications (prescription and non-prescription), treatments and therapies taken from screening through the last dose of study medication, including those initiated prior to the start of the study, must be recorded on the appropriate page of the subject documents. Record the dose, route of administration, indication, and the start and end date (when the medication was taken).

Permitted Concomitant Therapy:

The subject is required to continue on a concomitant stable dose of dupilumab treatment regimen throughout the study, given that they have been using the treatment for the minimum amount of time deemed necessary by the investigator to have experienced an inadequate clinical response. Once informed consent has been signed, subjects may not have additional atopic dermatitis medications prescribed outside of their existing atopic dermatitis treatment regimen listed at screening.

The following commonly used products are acceptable for use throughout the study: acetaminophen, loratadine, pseudoephedrine, guaifenesin, and calcium. Subjects must check with study personnel before initiating use of prescribed or over-the-counter medications during the study.

A nonmedicated emollient, i.e., Eucerin® cream (supplied by the study doctor), will also be allowed during the study; use must be stable throughout the study

Any patient found to have cellulitis on physical exam during the study will be treated with appropriate antibiotics. It is at the investigator's discretion whether the study drug will be continued or held.

Prohibited Concomitant Therapy:

- Use of any investigational medication
- Concomitant therapy with CYP450 enzyme inducers (e.g., rifampin, phenobarbital, carbamazepine, phenytoin), which may cause loss of efficacy of apremilast
- All atopic dermatitis therapies outside of the subject's existing treatment regimen at screening are prohibited

Treatment Compliance:

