Study personnel will review the instructions printed on the package insert with subjects prior to dispensing the study medication. New study medication will be dispensed according to the Schedule of Assessments. The subject will be instructed to return the study medication packaging, including any unused medication, to the study site at each visit for assessment of compliance. Subjects will be asked whether they have taken their medication as instructed at each study visit. Any problems with compliance will be reviewed with the subject.

Compliance will be assessed in two ways. Subjects will be responsible for returning unused study drug to the site. Pills will be counted to determine compliance. Subjects will also be responsible for recording the date and time they take the study drug in a medication diary. Compliance is defined as taking between 75%-125% of dispensed study medication.

Dupilumab injections will also be recorded in the medication diary.

Withdrawal/Termination criteria:

The following are considered sufficient reasons for discontinuing a subject from study drug:

- Adverse events that the investigator believes may cause severe or permanent harm or which rule out continuation of study drug
- Lack of therapeutic effect:
 - Subjects who experience a significant flare of atopic dermatitis, as defined by a sudden intensification of eczema, or as a diagnosis of erythrodermic atopic dermatitis may be discontinued from treatment and enter the observational follow- up phase of the study.
 - In addition, if the subject, in his or her opinion, feels that their disease is worsening or not responding to treatment, they may withdraw consent to participate.
- Subject withdraws consent
- Subject lost to follow-up
- Death
- Protocol violation

The reason for discontinuation will be recorded in the subject's medical records.

D. Risk/benefit assessment:

- 1. **Physical risk**: Physical risk includes potential side effects or unknown adverse events related to study medication. It is unknown how the combination of apremilast with dupilumab will affect subjects. Side effects may be worse or intensified on this combination. Subjects may be at a slightly higher risk of infection than those taking the drugs individually, but this is unknown. It is unknown if this combination will improve atopic dermatitis. AD could stay the same or get worse.

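### The primary analysis has no rule for prohibited atopic dermatitis therapy taken before Week 16, so some users count as apremilast responders or leave the denominator

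*Protocol*

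**What the plan says.** - **The ban.** Protocol, Prohibited Concomitant Therapy: "All atopic dermatitis therapies outside of the subject's existing treatment regimen at screening are prohibited". No consequence for the analysis follows there or elsewhere.
- **The endpoint.** Protocol, Statistical methods, Primary Endpoint: IGA is assessed at each visit, "with the primary endpoint being the proportion of patients with an IGA of 0 (clear) or 1 (almost clear) at Week 16". The general methods paragraph, which the SAP repeats, calls IGA 0 or 1 a clinical response to apremilast and sets no condition on other therapy.
- **The analysis set.** Protocol, Statistical methods, and SAP, Statistical Methods: "Efficacy analyses will only use data from participants who complete at least 16 weeks of study treatment".
- **Discontinuation.** Protocol, Withdrawal/Termination criteria, introduces its list with "The following are considered sufficient reasons for discontinuing a subject from study drug"; "Protocol violation" is one entry. The wording permits discontinuation and does not require it.
- **Missing data.** The one sentence on imputation sits under Secondary Endpoints and names no method.
- **Data available.** Prior/Concomitant Medications requires every medication from screening through the last dose of study drug to be recorded with indication and dates. The Schedule of Assessments reviews concomitant medications at every visit, including early termination.

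**The concern.** Subjects enter with IGA 2 or more despite dupilumab, the Protocol foresees flares, and its Alternatives section lists other available treatments, including topical corticosteroids. Some use of added therapy before Week 16 is therefore plausible. With no rule, the result for such a subject depends on whether an unblinded investigator keeps or discontinues the subject and, if kept, on an IGA that the added therapy may have improved.

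At stake is the meaning of the headline proportion. Clearance helped by another treatment can be reported as a response to apremilast, and a subject who needed other treatment can be taken out of the efficacy rate. The trial has one arm, so no control group shows how much the added therapy contributed. The problem also differs from ordinary dropout: a completer who used prohibited therapy has an observed Week 16 IGA, so counting early terminators as non-responders would not deal with that subject.

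**Working it through.** **Plan's own figures.** The documents give no expected response rate, dropout rate or frequency of prohibited use, so there is no stated figure to reproduce on this point. The only related numbers are up to 20 screened and 16 completers, which imply up to 1 − 16/20 = 20% combined screen failure and dropout. If both numbers are met, the number treated lies between 16 and 20.

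**What happens to a user under the current text**

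1. Completes 16 weeks with IGA 0 or 1: in the denominator, counted as a response.
2. Completes 16 weeks with IGA 2 or more: in the denominator, counted as a non-response.
3. Discontinued before Week 16: out of numerator and denominator.

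**Formula.** Let N be the number treated, r the responders who took no prohibited therapy, a the users on path 1 and c the users on path 3. Assume that everyone else completes.

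- Rate under the plan = (r + a)/(N − c)
- Reference rate (users are non-responders, all treated in the denominator) = r/N

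Since a and c cannot be negative, the plan's rate is never below the reference. With r above 0, the two are equal only when a = c = 0, that is, when every user is on path 2.

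**Illustration (all counts assumed): N = 18, r = 4, two users**

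| Path of the two users | Rate | Difference from 4/18 = 22.2% |
|---|---|---|
| Both complete, IGA 2 or more | 4/18 = 22.2% | 0 |
| Both discontinued | 4/16 = 25.0% | +2.8 points |
| One completes with IGA 0 or 1, one discontinued | 5/17 = 29.4% | +7.2 points |
| Both complete, IGA 0 or 1 | 6/18 = 33.3% | +11.1 points |

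**Sensitivity to the assumptions.** Take 16 subjects, 4 to 8 unaided responders and 1 to 4 users.

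- Users counted as responders: 1/16 = 6.3 points each, so +6.3 to +25.0 points.
- Users dropped: from +1.7 points (4/16 = 25.0% to 4/15 = 26.7%) to +16.7 points (8/16 = 50.0% to 8/12 = 66.7%).
- Users kept with IGA 2 or more: 0.

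**Precision.** With 6 unaided responders and 2 users among 16, non-responder handling gives 6/16 = 37.5% (95% CI 15.2 to 64.6). Counting both users as responders gives 8/16 = 50.0% (24.7 to 75.3). These are exact Clopper-Pearson intervals, an assumption because the plan names no method.

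**Does the direction depend on the comparator?** Yes. Suppose the comparator is the observed outcome and both users would have had IGA 0 or 1. Dropping them then lowers the rate, from 8/16 = 50.0% to 6/14 = 42.9%. If both would have had IGA 2 or more, dropping them raises it, from 6/16 = 37.5% to 6/14 = 42.9%.

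**The case against.** The strongest reply is that this is a small, largely descriptive study with safeguards in place. New atopic dermatitis prescriptions are barred after consent, subjects must check with staff before starting any medication, and the Safety section tabulates concomitant medications, the dropout rate and reasons for early termination. The discontinuation path follows from the completer rule and applies to any early termination. Counting the observed IGA regardless of other therapy is also a legitimate choice for some questions.

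Much of this stands. A reader might infer that every user inflates the rate; the documents do not support that, because a user who completes with IGA 2 or more stays in as a non-responder. Nor do they support reading the violation entry as forced withdrawal, or the bias as upward against every comparator. A withdrawn subject leaves the efficacy rate but not the report, since the reasons for termination are tabulated. The exact intervals are also far wider than the shift in the illustration.

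The gap itself remains. The tabulations do not alter the primary rate, and the unspecified imputation sentence cannot apply to a completer whose IGA was observed. If the observed IGA is the intended choice, the plan should say so. Since it labels the outcome a response to apremilast, non-responder handling fits its stated question better.

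Two practical objections also stand. A rule covering any added therapy turns one brief early use into non-response. And medication recording is required only through the last dose of study drug, so therapy begun after stopping but before Week 16 might not be captured.

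**Conclusion.** The concern holds in a limited form. Following the plan as written credits to apremilast a completer who reached IGA 0 or 1 with prohibited therapy, and removes from the rate a user discontinued before Week 16. Both give a higher rate than treating users as non-responders among all treated subjects; the third path gives no difference.

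The size cannot be determined from the documents. The figure of 0 to 11 points rests on an assumed 18 treated, 4 unaided responders and 2 users, with all others completing, and the lower end is a real possibility. A reader might take the non-zero rows as an established overstatement; they show only what could happen. With about 16 completers, one such subject moves the rate by about 6 points, so the rule should be fixed before the data are seen. It is a change that should be made, at modest priority given the descriptive aim.

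**What to change.** Amend the completer-only sentence in both the Protocol and the SAP so that, for the primary endpoint, all treated subjects are in the denominator and those without a Week 16 IGA count as non-responders. Without this amendment, the rule below would contradict the analysis set. Then add:

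> A subject who starts any atopic dermatitis therapy outside the screening regimen before the Week 16 assessment is a non-responder at Week 16. A sensitivity analysis uses the observed Week 16 IGA regardless of such use, with subjects who have no Week 16 IGA counted as non-responders.

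For subjects who stop study drug early, state that medications are recorded up to the Week 16 assessment if one is made. For everyone else the dates are already collected.

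The cost is one amended sentence in each document, the added text and one further line in the results. The reported rate may be slightly lower, and a brief early use counts against response; the sensitivity analysis shows how much that matters. The change affects analysis only and alters no rule on treatment or discontinuation.
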